**ABSTRACT (Objectives and Methodology of the Project)**

(Please only use the space provided below)

**General integrated goal of the coordinated project:**

To elucidate the role of succinate and other metabolites derived from the intestinal microbiota such as Short Chain Fatty Acids (SCFAs), as energy sensing metabolites in the context of obesity and type 2 diabetes (T2D).

**Specific objectives of Subproject 1 (SP1):** **1a.** - To investigate whether intermittent fasting (IF) is better than Continued Daily Caloric Restriction (DCR) in terms of metabolic improvement through the study of: 1) the dynamics of gastrointestinal hormones and energy sensing metabolites, 2) the intestinal microbiome, 3) variability on succinate and SCFAs, MCFAs and Biliary Acid after weight loss; **1b.** - To characterize the functional changes of adipose tissue mesenchymal derived stem cells (ASCs) in IF and DCR conditions according to the BMI of the donor (ex vivo study); **1c.** - To investigate the expression and secretory profile of ASCs according calorie restriction conditions.

**Methodology: clinical study: randomized, cross-over design**, study participants (n=15) will consume either lifestyle recommendations for a healthy Mediterranean diet under a continued caloric restriction diet (**DCR**) or will undertake an intermittent (**IF**) protocol. Clinical, anthropometrical and functional studies. Metabolomics for gut derived metabolites in plasma. Enterocrinology gastrointestinal dynamics. Metagenomic analysis.

## HEALTH RESEARCH PROJECTS

Application No.:  
PI20/00338

### HEALTH RESEARCH PROJECT APPLICATION FORM BACKGROUND AND STATE-OF-THE-ART

Project's aim, background and state-of-the-art of the scientific and technical knowledge, and national or international groups working in the same specific or related lines.

Please state references in the next item: Relevant references

Max. 3 pages (15,700 characters)

**Obesity and type 2 diabetes (T2D)** are directly responsible for a high percentage of mortality among “non-communicable diseases” (<https://www.who.int/news-room/fact-sheets/detail/noncommunicable-diseases>), with more than 2 million deaths annually worldwide. Their prevalence, despite all efforts to prevent and treat them, continue to increase relentlessly, becoming one of the main **health and social emergencies** for the healthcaresystems. There are many causes of this **epidemic**, and better understanding the reasons that lead to them is critical to better and more efficiently prevent and treat these diseases. Weight control is a crucial element involved in both diseases (obesity and T2D) and despite being the subject of study for decades, **its management** remains **elusive** in most interventions.

Many elements are involved in weight control, ranging from (a) alterations **of the energy balance** with high **inter-individual variability** [1,2] in terms of metabolic flexibility defining “**thrifty**” and “**non-thrifty**” phenotypes [3], (b) hormone mediators such as **FGF21** identified in animal models and suggested in associative studies of obese patients [4], (c) changes in **adaptive thermogenesis** although the **impact of brown tissue** in humans in energy expenditure is limited, (d) **genetic factors** with an effect on the overall result of energy expenditure, and (e) **energy sensors** responsible for establishing a direct link between energy expenditure and intake [5-8]. In this latter area, **new elements** are emerging as relevant players with a high potential to become useful tools both to better **understand the pathophysiological process** and to delineate useful **therapeutic approaches**.

#### *Energy sensing metabolites:*

There is increasing evidence that there is a direct relationship between energy expenditure and intake, as a key element in determining daily energy balance [7,8], through what is known as energy-sensing mechanisms [7]. These mechanisms, which are still little known, may include **biological mediators** such as certain **hormones** like myokines, adipokines and **metabolites** such as **glucose** itself, **bile acids** or **free fatty acids** with a central action on intake regulatory centers [9]. The **maladjustment** between **nutrient availability and cell energy requirements** is a key factor contributing to the development of **obesity** and **T2D**. **Dynamic exchanges of intra- and extracellular metabolites are crucial** to duly integrate and **coordinate** the biological network in cells, particularly **the concentration of nutrients and intermediate metabolites** [10].

#### *Succinate may have a new role in energy sensing:*

There is wide evidence that succinate is a **pleiotropic metabolite** that works not only as an energy intermediate but also as a signalling metabolite both in cytosol, but also and extracellularly through its cognate receptor **SUCNR1** [11]. Although it has been long been described as a danger signal, recently, in the context of energy homeostasis, succinate has shown to be an antilipolytic factor [12], a potent activator of thermogenesis [13] and a regulator of intestinal gluconeogenesis [14, 15]. Recently, we have demonstrated that **succinate** acts as a new **signaling metabolite** that **controls the resolution of inflammation**, a physiological **circuit that is broken in obesity**. Thus, we have observed that SUCNR1 deficiency in macrophages induces *in vivo* inflammation, glucose intolerance and cell metabolic stress [16]. **High levels of circulating succinate** have been mainly described in pathological conditions [17-20], including **obesity and T2D** [17,18]. Therefore, it is not unreasonable to suggest that obesity may be associated with a **resistance to succinate** as occurs with other hormones such as insulin or leptin [21,22], favoring a vicious circle of higher succinate levels, greater succinate resistance, which has already been proven in terms of its effects on the resolution of

## HEALTH RESEARCH PROJECTS

inflammation [16]. However, circulating succinate does not only increase in diseases and data from previous studies also **describe higher levels of succinate** in some physiological conditions, such as **enduring exercise** [23].

Therefore, despite all the available information, the physiological role of succinate in the energy balance and in the pathophysiology of obesity and related diseases needs to be clarified. In fact, the **main source of succinate circulating levels** is so far **unknown**, but there is strong evidence pointing to the **intestine** as one of the **relevant contributors** to blood levels, through differences in the composition of the microbiota [18].

### *Circulating succinate as a biomarker of metabolic health:*

This metabolite is an excellent marker of cell state as it occupies a key position in the metabolism, being the only mediator between the tri-carboxylic acid cycle and the mitochondrial respiration chain through complex I. **Succinate** is a good marker of cell damage and circulating levels have been used as predictors of **poor prognosis** in critically ill patients, and as a marker of **ischemia and inflammation**. When mitochondrial dysfunction occurs, as has been proved in metabolically active tissues in obesity and T2D, mitochondrial succinate levels increase, and subsequently extracellular levels could also increase [24, 25]. Thus, in a pathological context **circulating succinate** might be **sourced from both damaged tissues and gut microbiota**.

Our results [26] point to **succinate** as a metabolite capable of **representing** at the same time various components of the metabolic state, offering a broader vision of **energy homeostasis**, contained in a single, easily measurable **marker**.

### *Succinate, a metabolite regulated by dietary intake:*

Metabolomic analysis of plasma after a meal shows an increase in succinate, pyruvate, and lactate, indicating a postprandial shift in the body's energy source from  $\beta$ -oxidation to glycolysis [27]. Interestingly and similarly to what happens with some gastrointestinal hormones, we have seen that **this metabolite** presents a **response after food intake** and that this response is **dependent** on both the type of **nutrient** and the **route of administration**, indicating that it has a clear nutritional regulation. Thus, we have observed that there is a **peak** in circulating levels 60' **after a standard meal test**, which is **reproduced** after administering **glucose orally**, unlike what happens when it is administered intravenously, (*preliminary data submitted in Diabetes Care 2020, annex figure 1*). This indicates that the higher levels of circulating succinate after food ingestion are not only consequence of glycolysis and intestine play a key role.

The physiological significance of this dynamic of succinate related to intake requires further investigation. In this regard, the **new concept** that energy sensing metabolites act as **signaling molecules** with **extracellular functions** beyond energy obtention is gaining prominence. In fact, it has been postulated for some molecules such as **short-chain fatty acids (SCFAs)** from the intestinal **microbiome**, which can regulate the energy metabolism in the host by exerting an autocrine-paracrine signal on adipose tissue with an **anti-lipolytic effect** [28,29] mediated by the attenuation of the effect of **hormone-sensitive lipase (HSL)**, besides other metabolic effects.

### *Effect of weight loss on succinate levels:*

In addition to intake and dysmetabolic situations, **circulating levels** are also likely to undergo **changes** after weight loss. Severely obese patients, with and without dysglycemia, are able to reverse high circulating levels **after weight loss** [26]. In these patients, decreased circulating levels are paralleled with a restoration of the "**physiological**" response after food ingestion observed in non-obese subjects (*Submitted in Diabetes Care, figure 2*). Interestingly, this behavior is **highly like** what we observe with **incretin hormones** after a meal ingestion. This supports the conceptual hypothesis that succinate is a good marker of metabolic health, which can be especially useful as a **biomarker** in certain circumstances as we have already noted in the case of **diabetes remission** following metabolic surgery [26].

In summary, among the mechanisms involved in weight control, energy sensing metabolites are opening new paths to help better understand the concept of metabolic flexibility and propose new therapeutic approaches in diseases such as obesity and diabetes. In this field, typically intracellular energy metabolites such as succinate are now being considered relevant in their extracellular signalling function through their specific receptor in metabolically sensitive

## HEALTH RESEARCH PROJECTS

tissues. To date we have sufficient preliminary evidence supporting this function, with data that clearly point to a nutritional response and a more-than-likely intervention of the intestinal flora in plasma regulation.

### *Specific proposal subproject 1:*

#### Weight loss

**Daily calorie restriction diets (DCR)** and more recently, diets that incorporate **intermittent fasting (IF)**, are suitable methods that can reduce obesity and its associated comorbidities including T2D [30]. Both (DCR and IF), have shown **similar efficacy** in improving body composition, reducing cardiovascular risk factors, improving glycemic control, insulin sensitivity and insulin secretion. The **benefits of hypocaloric diets** are dependent on **weight loss capacity and on the degree of fat mass reduction**. However, diets involving **IF**, particularly those adapted to the individual's **circadian rhythm (eTRF early-time-restricted-feeding)**, can achieve similar **benefits even without weight loss** [31,32].

#### Metabolic switch

During **fasting periods**, triglycerides are broken down to **fatty acids** that are **converted** by the **liver and gut** epithelial cells in **ketone bodies** during both b-oxidation to acetyl -coenzyme A (CoA) and/or conversion of ketogenic amino acids, and are **released into the bloodstream** to provide **metabolic fuel** to various organs [33]. Ketone bodies begin their increase in plasma within 8 to 12 hours after the onset of fasting, reaching levels as high as 2 to 5 mM by 24 hours [34]. **Ketone bodies** are not just fuel used during periods of fasting but also **act as signaling molecules** with relevant cellular and organ effects. Ketone bodies **regulate the expression and activity of many proteins and molecules**. These include peroxisome proliferator -activated receptor  $\gamma$  coactivator 1 $\alpha$  (PGC-1 $\alpha$ ), nicotinamide adenine dinucleotide (NAD $+$ ), fibroblast growth factor-21, sirtuins, poly-adenosine diphosphate [ADP] -ribose) polymerase 1 (PARP1) and ADP ribosyl cyclase (CD38) [35-39], among others. All of these changes drive the switch on systemic metabolism.

#### Health benefits of intermittent fasting

As commented above, many studies have indicated that several of the **benefits of IF** are **dissociated** from its effects on **weight loss**. In the recent work by Sutton EF et al. in pre-diabetic patients, all classic metabolic parameters except triglyceride levels improved during intermittent fasting, without weight loss [40]. Most organ systems respond to **IF** to enable the organism to overcome the challenge and **restore homeostasis**. Intermittent fasting **induces an adaptive stress response** leading to an increase in cellular DNA repair mechanisms, protein quality control, antioxidant defenses, mitochondrial biogenesis and autophagy, and inflammation [41]. Although we do not fully understand the precise mechanisms, the **beneficial effects of IF** have been attributed to a **metabolic switching** and an improvement in the cellular response to a persisting stress. Notably, although it is widely thought that changes in the microbiome might explain some of the beneficial effects of IF, nowadays **no in-depth analysis** have been done to address the effects on **gastrointestinal hormones, energy sensors and the microbiome**. Studies in **animal models** demonstrate an **improvement in systemic inflammatory parameters and in adipose tissue with improved thermogenic** [42] **response** and the **restoration** of the dynamics in **intestinal flora** improving metabolic [43] health, when subjected to IF. We know today that **commensal bacteria** and **their metabolites** have the potential to exert **pro- or anti-inflammatory effects** regulating the immune response in the **intestinal wall** [44]. Finally, these changes may have **systemic effects**, as already described in some autoimmune and neurological [45] diseases. Continued low-calorie dieting has clear systemic anti-inflammatory effects [46], although changes in the microbiome are less clear. In **our series** of patients put on **continued low-calorie dieting for 6 months** with effective weight loss, an **improvement** is noted in **all metabolic parameters** but with great **interindividual variability in the microbiome** between before and after weight loss (*preliminary data attached, figure 3*). Changes during IF have only been explored in **animal models** with an **increase** in the relative abundance of **bacteria associated with the synthesis and degradation of ketone bodies** and metabolic pathways involved in the **glutathione metabolism** [47], which could favour **antioxidant pathways** that would eventually influence the host.

## HEALTH RESEARCH PROJECTS

### HEALTH RESEARCH PROJECT APPLICATION FORM HYPOTHESIS AND OBJECTIVES

(Please only use the space provided below)

#### HYPOTHESIS

*Summary of evidence:*

Energy sensing metabolites are emerging as being crucial in the relationship between energy expenditure and intake. They are responsible for the proper integration and coordination of the biological network in cells, particularly the concentration of nutrients and intermediate metabolites, key elements in the pathogenesis of obesity and T2D.

#### OBJECTIVES

**General integrated goal of the coordinated project:**

To elucidate the role of succinate and other metabolites derived from the intestinal microbiota such as SCFAs, as energy sensing metabolites in the context of obesity and T2D.

#### Specific objectives of Subproject 1 (SP1)

1a. - To investigate whether IF is better than DCR in terms of metabolic improvement through the study of:

- 1) the dynamics of gastrointestinal hormones and energy sensing metabolites
- 2) the intestinal microbiome
- 3) variability on succinate and SCFAs MCFAs and BA after weight loss

## HEALTH RESEARCH PROJECTS

Application No.:  
PI20/00338

### HEALTH RESEARCH PROJECT APPLICATION FORM METHODOLOGY

Design, study subjects, variables, data collection and analysis, study limitations.

#### Task 1:

##### Human study protocol:

A pilot clinical trial in human study participants will be assayed. Participants for intermittent fasting (IF) will be asked to fast for 24 hours on two days of the week (2/5 protocol).

##### 1A.-Design:

Utilizing a **randomized, cross-over design**, study participants (n=15) will consume either lifestyle recommendations for a healthy Mediterranean diet under a continued daily caloric restriction diet (**DCR**) or will undertake an intermittent (**IF**) protocol. **Each study period** will be **8 weeks** - total study period will be **16 weeks + a 4-week washout** period between dietary exposures. The study participants will be **adults** who have obesity with a Body Mass Index (**BMI**)**25 kg/m^2 and 40 kg/m^2** and have no contraindications for intermittent fasting (see inclusion and exclusion criteria below).

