### 1B.b-Meal Test and study of gastrointestinal hormones:

Before and after each restriction diet (DCR and IF diet) at the beginning and at the end of each period (4 test). 200ml administration of Isosource Energy (Novartis, Switzerland) containing 398kcal (50% carbohydrates, 15% proteins and 35% lipids). Extraction at 0, 15, 30, 60 and 120 minutes. Determination of Plasma concentrations of glucose, insulin, GLP-1 and using the Elisa kit (EZGLP1T-36K EMD Millipore, ThermoFisher) and succinate (EnzyChrom™ Succinate Assay Kit (BioAssay Systems, USA)

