**Statistical analysis:**

Strategy of the main statistical analysis: The data will be shown as percentages (categorical variables), means +/- standard deviation (continuous variables with normal distribution) or median with interquartile range (continuous variables with

non-normal distribution). The normality of the variables will be analysed with the Kolmogorov-Smirnoff test. To perform the Comparisons of each pre and post intervention group test for paired data will be used. To compare variables The McNemar test (paired data) will be used categorically / qualitatively. The continuous variables of normal distribution will be analysed with the Student t-test for paired data. For continuous variables that do not follow a normal distribution, first we will try to normalize by means of their logarithmic transformation to use parametric tests; if not, non-parametric tests for paired data (Wilcoxon T) will be used. The increase in concentrations of GLP-1 and succinate in response to dynamic functional tests will be measured by calculating the area under the curve. The correlations between the variables will be analysed with the Pearson or Spearman correlation coefficients, when appropriate. Multivariate analysis will be used to predict the clinical and/or functional variables that determine the improvement of clinical and metabolic variables after each diet protocol. Possible confusing variables or effect modifiers (interaction) will be selected based on clinical criteria (data from previous literature) and in function of the result of the univariate analysis ( $p < 0.20$ ). All calculations will be performed with the STATA software package (v13.1 for Mac; StataCorp LP, College Station, Texas) and a value of bilateral  $p < 0.05$  will be used as significant.

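### The planned paired pre/post tests ignore period and the period-2 baseline, so residual effect from the first diet could shrink each diet's estimated effect and, under stated conditions, bias the IF-DCR comparison

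*Combined protocol and SAP*

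**What the plan says.** Section 1A (Design) describes a "randomized, cross-over design" in 15 participants. Each diet lasts 8 weeks, and the duration is given as "16 weeks + a 4-week washout", the washout being the "period between dietary exposures". The length of the washout is not justified. Objective 1a is comparative: "To investigate whether IF is better than DCR in terms of metabolic improvement through the study of" gut hormones, microbiome and circulating metabolites.

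The state of participants at the start of period 2 is measured. Section 1B.b places the meal test "at the beginning and at the end of each period (4 test", and section 1B takes blood before and after each diet period. Section 1A.c lists weight and other anthropometry without visit times.

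For the analysis, the annex says: "To perform the Comparisons of each pre and post intervention group test for paired data will be used". It then names the paired t-test, Wilcoxon and McNemar tests, areas under the curve, correlations and a multivariate prediction analysis, with two-sided significance at 0.05. The supplied text has no direct IF-versus-DCR test, no period or sequence term and no comparison of the two starting values.

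**The concern.** A paired pre/post test for one diet pools people who took it first with people who took it second, as if both groups started from the same state. The protocol's background gives reason to doubt this. It says that, after losing weight, people with severe obesity "are able to reverse high circulating levels" of succinate and regain a normal response to a meal, and both are outcomes here. If part of the first diet's effect is still present when the second diet starts, the second diet's starting value is already shifted.

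Carry-over could also be unequal. The Weight loss section ties the benefit of hypocaloric diets to weight and fat loss, but says fasting regimens can give similar benefit without it. That would affect the comparison of diets, which is the question the trial asks.

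**Working it through.** **Inputs from the documents.** Two 8-week periods, a 4-week washout, at least 15 participants, 20% dropout, two-sided 0.05. No effect size, SD, power or sequence allocation is given, so 15 cannot be reproduced from a power formula. Only the dropout arithmetic can be checked: 15 × 0.8 = 12 completers if 15 are enrolled.

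**Assumption.** A fraction r of the first diet's effect remains at the start of period 2. The documents give no figure; I use 0.25 to 0.75. Both diets' true pre/post effects are set to 1.

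**Step 1: each diet's pooled pre/post effect.** If end values depend only on the current diet, the period-2 change is 1 − r. With half the participants taking the diet second, the pooled effect is ½(1) + ½(1 − r) = 1 − r/2.

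| r | Understatement |
|---|---|
| 0 | 0% |
| 0.25 | 12.5% |
| 0.50 | 25% |
| 0.75 | 37.5% |

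If the residual instead persists unchanged through period 2, it sits in both the before and after values and cancels. The change is then 1, with no understatement.

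**Step 2: IF minus DCR on changes, equal sequence sizes.** IF is reduced by r_DCR/2 and DCR by r_IF/2, so the bias is (r_IF − r_DCR)/2.
- Equal carry-over: 0.
- r_IF = 0.25, r_DCR = 0.75: (0.25 − 0.75)/2 = −0.25 of a diet effect, against IF.

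If the residual persists to the end of period 2 and end values are compared, the bias has the opposite sign: (r_DCR − r_IF)/2 = +0.25 for the same values.

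**Step 3: unequal sequence sizes, no period term.** With n₁ taking IF first, n₂ taking DCR first and N = n₁ + n₂, the bias on changes is (n₁·r_IF − n₂·r_DCR)/N. For equal carry-over of 0.5:
- 8 vs 7: (4 − 3.5)/15 = +0.03
- 7 vs 5: (3.5 − 2.5)/12 = +0.08
- 8 vs 4: (4 − 2)/12 = +0.17

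Averaging the two sequence means, which is what a period term does, brings each of these to 0. It leaves the −0.25 of Step 2 in place.

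**Step 4: is imbalance likely?** Suppose 8 vs 7 are randomised and three are lost at random. A 6 vs 6 split needs two losses from the eight and one from the seven: 28 × 7 = 196 of the 455 possible sets of three, or 43%. Unequal sequences therefore occur in 259/455 = 57%. The 8 vs 4 split is rare: 35/455 = 8%.

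**Step 5: what a check could show.** With 6 vs 6 completers, a two-sided 0.05 test for unequal carry-over has 12% power at a difference of 0.5 SD and 35% at 1.0 SD. The period-1-only 95% half-width, before baseline adjustment, is t × √(1/n₁ + 1/n₂):
- 8 vs 7: 2.16 × √(1/8 + 1/7) = 1.12 SD
- 6 vs 6: 2.23 × √(1/6 + 1/6) = 1.29 SD

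**The case against.** The strongest reply is that nothing shows carry-over occurs. The succinate passage concerns severe obesity, and the work it cites is linked to metabolic surgery; it says nothing about how long an effect lasts after an 8-week diet stops in people with BMI 25 to 40. The remark that fasting helps without weight loss singles out early time-restricted feeding, which is not the two-fast-days scheme used here. The order is randomised, a washout is present, and each period has its own baseline. All this stands: r is assumed and may be near zero.

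A reader might infer that the plan never deals with carry-over. The documents do not support that. The Methodology form refers to a limitations and contingency section in the annex, and that section is not in the supplied text. The statement that can be made is about the Statistical analysis text, which is present and silent.

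A reader might also infer that any carry-over biases both the pre/post effects and the diet contrast. Steps 1 and 2 show otherwise. The understatement disappears if the residual persists unchanged, and equal carry-over with equal sequences leaves the contrast unbiased.

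Pilot status lowers the stakes. It does not remove the point, because significance tests at 0.05 are planned and the results are meant to guide larger studies.

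**Conclusion.** The point holds as a gap in the analysis, not as a demonstrated bias. The supplied plan collects period-2 starting values for blood and the meal test but does not use them to check return to baseline, and it gives no period-adjusted estimate of the contrast in objective 1a.

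The r/2 understatement rests on three assumptions: the assumed r, equally effective diets in balanced sequences, and end values that depend on the current diet alone. Bias in the contrast needs either unequal carry-over (0.25 of a diet effect in the example) or unequal sequences without a period term (0.03 to 0.17 at r = 0.5). The second condition is more likely than not with 20% dropout and is easily removed. The first cannot be removed by modelling period; it can only be examined, and imprecisely. The change is worth making because it is cheap.

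**What to change.** Leave the diets, washout and visits as they are and amend the Statistical analysis text:

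1. Report period-2 minus period-1 baseline by sequence, with confidence intervals, for HOMA-IR, fasting succinate and the meal response. Add weight if it is recorded at the start of each period, and state that timing in section 1A.c.
2. Estimate IF minus DCR directly within person with a period term, for example by comparing within-person period differences between the two sequences. State in advance whether changes or end values are used, because residual effect acts on them differently. State that this does not remove unequal carry-over. A model with several baseline covariates would be heavy for about 12 completers.
3. Report a period-1-only, baseline-adjusted estimate with its confidence interval as a sensitivity analysis. Do not use a carry-over test to choose the main analysis; its power is too low.

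The cost is wording and a small amount of analysis, on data that are already planned except possibly weight. The downside is precision: before baseline adjustment, the period-1-only half-width is about 1.1 SD with 8 vs 7 and about 1.3 SD with 6 vs 6 completers, so it will rarely settle the matter alone.
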